7.8.14 Faecal Calprotectin Stool Samples

A faecal sample will be taken to measure faecal calprotectin at the time points indicated in Schedule of Events section. Information on sample processing will be provided in the Laboratory Manual.

7.8.15 Genetics/Pharmacogenomics Sample (for optional genetic research)

A 6ml blood sample for DNA isolation will be collected from patients who have consented to participate in the genetic analysis component of the trial. Participation is optional. Patients who do not wish to participate in the genetic research may still participate in the trial.

In the event of DNA extraction failure, a replacement genetic blood sample may be requested from the patient. An additional signed ICF will be required to obtain a replacement sample unless it was included in the original consent.

See Appendix 8 for information regarding genetic research. Details on processes for collection and shipment and destruction of these samples can be found in the Laboratory Manual.

7.8.16 Additional Research Samples (Biomarkers)

Biomarker(s)/Pharmacodynamics Biomarker

For all patients, blood serum samples will be collected as is scheduled in the Schedule of Events table. Please see the Laboratory Manual for further information.

Novel disease associated candidate biomarkers and those subsequently discovered as a response to the action of associated with action of GSK1070806 may be identified by application of

- gene expression analysis, which may be conducted on the blood and/or colon tissue biopsies RNAsequencing and/or alternative equivalent technologies. This facilitates the measurement of relative abundances of RNA species resulting in a transcriptomic profile of each blood and/or tissue sample
- analysis of soluble inflammatory mediators in the blood including but not limited to, pro-inflammatory and anti-inflammatory cytokines and chemokines

Table 7 : Immunology Tests

Immunology	CXCL-10	Exploratory endpoints
	IFN-Υ	
	CRP	
	IL-6	
	IL-18	

In relation to Immunology based testing, individual markers maybe evaluated using multiple sample types see Table **8** for summary.

Table 8 Immunology blood tests

Immunology	TNF- α	Safety
	IFN-Υ	
	IL-6	

7.8.17 Liver Chemistry Management

Since participants will receive a single dose of trial medication, there are no liver-specific stopping criteria as such (although opportunities for an independent committee to review general safety data and, if necessary, advise the trial be stopped are detailed in Section 12.6). In the event of liver parameters deviating from the thresholds described in Appendix 6, follow instructions in that section.

Liver chemistry increased monitoring criteria have been designed to assure subject safety and evaluate liver event aetiology (in alignment with the FDA premarketing clinical liver safety guidance). http://www.fda.gov/downloads/Drugs/GuidanceComplianceRegulatoryInformation/Guidances/UCM174090.p df

7.9 Sample Collection (Tissue, Blood and Stool samples)

7.9.1 Tissue sample collection Formalin fixed and samples for gene expression analysis

Up to 12 biopsies will be taken from the lesioned and non-lesioned region of the tissue at the pre-dose visit and at Visit 8 (week 12) post treatment with GSK1070806. Tissue samples will be divided accordingly for histological assessment and gene expression analysis as feasibility dictates. A variety of techniques including immunohistochemistry and quantitative polymerase chain reaction may be used. Details of biopsy sample collection processing, storage and shipping procedures are provided in the Laboratory Manual.

Samples for paraffin embedding will be immediately placed in 10% neutral buffered formalin. Samples will then be shipped within 48 hours of collection to the Exploratory Biomarker Assay Laboratory at GSK (Collegeville, PA, USA) in accordance with the Laboratory Manual.

Samples for gene expression analysis will be immediately placed in 5ml tube containing RNA later. Specific sample collection kits, shipping containers, and airway bills and associated courier service will be provided specifically for this purpose by GSK.

7.9.2 Biopsy collection/colonoscopy known procedure related risks

Endoscopy will be performed during screening and at week 12 after dosing. This is standard of care procedure in CD. Colonoscopic assessment after drug administration to check endoscopic response is also often part of standard clinical practice. A colonoscopy is usually safe but in rare cases it can cause harm to the bowel. About 1 person in every 400 has bleeding after their colonoscopy but it is usually easy to stop. Bleeding is more common if a polyp is removed, but rare if biopsies are taken. Rarely, the bleeding is more difficult to stop and means that the person needs to be admitted to hospital. This happens to about 1 in every 2000 people having a colonoscopy. Even more rarely, colonoscopy can cause a small tear (perforation) in the bowel. This happens to about 1 in every 2500 people having a colonoscopy. If a patient received sedation for colonoscopy, hypoxia may occur rarely, but patients are constantly under monitoring.

7.9.3 Blood samples

7.9.3.1 Pharmacokinetic and pharmacodynamics samples

For all patients, blood samples for the determination of GSK1070806 serum levels will be collected as is scheduled in the Schedule of Events table / Section 7.8.9 of study protocol. Please see the latest version of the Laboratory Manual for further information.

7.9.3.2 Safety assessment samples

Samples will be taken for both Haematology and Biochemistry testing (see Section 7.8.8). These samples will be processed in the local hospital laboratory as per standard practice. This information will be recorded in the appropriate sections of the case report form and individual patient's medical records.

All safety assessment results (including but not limited to blood tests) will be reviewed by the local medical team and acted on in accordance with the local standard practice. Any corrective / clinical action required in relation to any of these safety tests will be documented in the patients' medical records as well as the appropriate section of the case report form.

7.10 Supportive Treatment

The risk of infusion reactions to GSK1070806 is judged by both GSK and the study sponsor to be low based on previous clinical experience.

Due to the current relatively low numbers of patients exposed to the study drug, the theoretical risk of individual patient drug infusion reactions remains, it is for this reason that the following precautions will be undertaken;

- 1. Investigators/site personnel will be made aware of the risk of hypersensitivity reactions; which may present as an infusion reaction, and will monitor patient closely for a minimum of 3 hours post END of INFUSION
- 2. Investigational product will administered by the Investigator/site personnel prepared to manage infusion reactions and anaphylaxis, following their standard practice to manage any untoward infusion reactions noted during or after the infusion period.

3. For subjects with a history of allergies (allergic responses to food, drugs, insects, or a history of urticaria), chlorphenamine or equivalent (12.5-50 mg based on clinical judgement) or equivalent and paracetamol maybe administered prophylactically prior to dosing. Antihistamine H2-receptor antagonists (e.g. ranitidine) are also permitted.

7.11 Concomitant Medication

7.11.1 Permitted Concomitant Medications

The pharmaceutical/ trade name, dose, route of administration, indication and start/ stop date of each medication the patient takes during the trial will be recorded. New medications or changes to current medications during the trial will also be recorded. Permitted concomitant medications for participants are as follows:

- Oral Corticosteroids: For participants receiving prednisone, or equivalent, the dose must be ≤20mg/day for ≥4 weeks prior to screening and planned to remain stable for the duration of the trial. For participants receiving budesonide the dose must be ≤6mg/day for ≥4 weeks prior to screening and planned to remain stable for the duration of the study
- 2. Immunosuppressant and other CD medications: For participants receiving azathioprine, methotrexate, or 6-mercaptopurine for CD, the dose must be stable for >8 weeks prior to screening and planned to remain stable for the duration of the study. For participants receiving methotrexate or 5-aminosalicyclic acid for CD, the dose must be stable for >4 weeks prior to screening and planned to remain stable for the duration of the study.
- 3. All other medications including over-the-counter medicines, supplements, vitamins and herbal remedies that each participant is taking at the time of consent will be permitted and recorded.

If there is adequate documentation of an undetectable drug level measured by a commercially available assay for any of the approved biologics (infliximab {Remicade}, adalimumab {Humira}, vedolizumab {Entyvio} ustekinumab {Stelara}, there is no minimum washout prior to Baseline. However in the absence of adequate documentation of undetectable drug levels, a washout period of 8 weeks will be necessary between the last dose of infliximab, adalimumab, vedolizumab and baseline. For ustekinumab the washout period will be 12 weeks.

7.11.2 Prohibited Medications and Non-drug Therapies

If any Subjects who start prohibited medications or therapies at any time during the trial, these individual patients circumstances should be discussed with the trial team (Sponsor- clinical coordinator). As the trial only includes a single dose of GSK1070806 is administered on Day 1, trial subjects should continue with the study assessments and be closely followed up for safety.

The following medications and therapies are prohibited at any time during the trial;

- 1. Use of other investigational agents (biologic or non-biologic, or non-drug therapy; investigational applies to any drug not approved/licensed for use in the country in which it is used).
- 2. Use of parenteral glucocorticoids within 4 weeks prior to randomisation.
- 3. Use of cyclosporine, tacrolimus, sirolimus or mycophenolate mofetil within 4 weeks prior to start of therapy
- 4. Use of intravenous antibiotics within 2 weeks prior to start of therapy

- 5. Prior use/exposure to aTNF or vedolizumab is allowed but this therapy should have been discontinued a minimum of 8 weeks (last dose given) before randomisation. If there is adequate documentation of an undetectable drug level measured by a commercially available assay, there is no minimum washout prior to Baseline
- 6. Prior use/exposure to ustekinumab is allowed but this therapy should have been discontinued a minimum of 12 weeks (last dose given) before randomisation. If there is adequate documentation of an undetectable drug level measured by a commercially available assay, there is no minimum washout prior to Baseline

7.11.3 Vaccines

Live, attenuated or recombinant vaccines are not permitted 60 days prior to GSK1070806 administration or within 90 days of treatment with GSK1070806. Typical examples of excluded vaccinations include *(but not limited to)*:

- Nasal flu vaccines Fluenz Tetra ™
- Yellow fever vaccine commonly required for travel (https://www.cdc.gov/yellowfever/vaccine/index.html)

In the NHS -UK there is a well-defined vaccination program, further details can be found here:

http://www.nhs.uk/Conditions/vaccinations/Pages/vaccination-schedule-age-checklist.aspx

Please refer to the individual vaccination summary of product characteristics (SmPC) for additional information and/or contact the Trials Office clinical coordinator for additional advice.

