Pro-IL-18, the natural cellular precursor, is cleaved by Caspase-1 or proteinase 3 to generate a biologically active mature 18 kDa protein. Mature IL-18 binds to the IL-18R α subunit resulting in the recruitment of IL-18R β on the cell surface. The interaction between IL-18 and the heterodimeric cell surface receptor induces signalling

pathways shared with other IL-1R family members such as Toll-like receptors and IL-1 receptors. IL-18 is expressed by macrophages, dendritic cells, osteoclasts, synovial fibroblasts, adipocytes, and epithelial cells. Whereas, the IL-18 receptor (IL-18R) is predominantly expressed on macrophages, lymphocytes, neutrophils, natural killer cells (NK), endothelial, epithelial and smooth muscle cells. In vivo, the binding of IL-18 to IL-18R complex is regulated by IL-18 binding protein (IL-18BP). IL-18BP is a naturally occurring protein which is constitutively expressed and secreted and binds with high-affinity to IL-18 (dissociation constant of 400 pM) neutralising it's biologic activity (Novick, Kim et al. 1999) (Kim, Eisenstein et al. 2000). IL-18BP is specific for mature IL-18 and does not bind the IL-18 precursor when assessed by Enzyme Linked Immunosorbent Assay (ELISA) (Novick, Schwartsburd et al. 2001) or BiaCore binding (Kim, Eisenstein et al. 2000). With the exception of IL-1F7 (Bufler, Azam et al. 2002), IL-18BP does not bind to other members of the IL-1 family or several cytokines tested.

One of the key biological functions of IL-18 is its role in host defence against microbial pathogens. IL-18 primes both innate and acquired immunity to viruses and other intracellular pathogens through activation and differentiation of Th1 and NK cells, the production of the pro-inflammatory cytokine IFN- γ , upregulation of Fas and Fas ligand, and also potentiation of other proinflammatory mediators. Studies in mice in response to challenge with the intracellular pathogen Mycobacterium avium have shown a strong requirement for a Th1 response and a role for IL-18 in the expulsion of the pathogen(Takeda, Tsutsui et al. 1998).

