1.2.3 Choice of treatment

Single induction dosing of GSK1070806 given intravenously at a dose of 10 mg/kg is proposed for the trial.

A wide range of doses of GSK1070806 were investigated in the clinic so far;

- Single dose of GSK1070806 from 0.008 mg/kg up to 10 mg/kg in healthy volunteers and from 0.25 mg/kg to 3 mg/kg in obese participants;
- Two repeat doses of either 0.25 or 5 mg/kg 28 days apart in patients with type2 diabetes
- Single dose of 3 mg/kg in the renal transplant study.

These doses have been well tolerated with an acceptable safety profile.

As targeting IL-18 in CD patients is an unprecedented mechanism, a dose of 10 mg/kg has been selected to fully test the mechanism of action. This dose is predicted to maximise pharmacological and clinical effects, based on the ex-vivo pharmacodynamics effects that were observed in the whole blood stimulation assay during the first treatment in human (FTIH) trial in healthy and obese participants (NCT01035645), while also taking into account the change in the population studied. Maximum effect was observed up to day 56 in particular on IFN- γ with no clear differentiation between 1 and 3 mg/kg in healthy volunteers. Suppression of IL-18 in plasma was achieved at significantly lower doses, with 99.9% occupancy sustained for 90 days at a dose of 0.3mg/kg in the FTIH study. Simulations using a physiologically based pharmacokinetic model based on the two pore hypothesis predict that a dose of 10 mg/kg is required to maintain >99% IL-18 suppression in the gut interstitium for 90 days, while >90% suppression can be achieved with a dose of 1 mg/kg.

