- 18. Use of any investigational drug within 30 days prior to screening, 5 half-lives or twice the duration of the biological effect of the investigational product (whichever is longer)
- 19. Participant has received live, attenuated or recombinant vaccine(s) within 2 months of randomisation or will require vaccination within 3 months of trial drug infusion
- 20. Any patients that are receiving medication(s) detailed in Section 7.11.2 of the trial protocol, will not be eligible for randomisation into the trial

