6.1.1 Protocol waivers or exemptions

Protocol waivers or exemptions are not allowed with the exception of immediate safety concerns. Therefore, adherence to the trial design requirements, including those specified in the schedule of events table, the trial protocol are essential and required for trial conduct. Any deviation from protocol procedures should be documented as a protocol deviation on the appropriate case report form (CRF).

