7.13.6 Follow-up Visit 9 (Day 112 +/- 7 days. Week 16)

- Clinical assessment
- Vital signs (heart rate, blood pressure, oral body temperature (°C), respiratory rate, (all taken in supine position)
- Physical examination
- Biochemistry bloods (see Section 7.8.8)
- Haematology bloods (see Section 7.8.8)
- Pharmacodynamics
- CDAI
- Immunogenicity blood sample
- Patient Daily Diary
- Adverse Event/SAE reporting
- Record of patient concomitant medication
- Blood sample (serum) for additional research

7.13.7 Follow-up / End of Study Visit 10 (Day 168 +/- 7 days. Week 24)

- Clinical assessment
- Vital signs (heart rate, blood pressure, oral body temperature (°C), respiratory rate, (all taken in supine position)
- Pregnancy test
- 12 lead ECG
- Biochemistry bloods (see Section 7.8.8)
- Haematology bloods (see Section 7.8.8)
- Pharmacokinetics/Pharmacodynamics
- CDAI
- Immunogenicity blood sample
- Patient Daily Diary
- Faecal calprotectin (patient stool sample)
- Adverse Event/SAE reporting
- Record of patient concomitant medication
- Blood sample (serum) for additional research

NB: All visit dates / times are related to Visit 3 (Day 1). If a visit is delayed for any reason the next visit date will be scheduled in relation to Visit 3. There are no planned treatment delays. If a drug infusion visit cannot be performed within the required timeframe, every attempt should be made to administer the infusion as close as possible to the permitted time window. In extreme situations, protocol-scheduled visits may be cancelled and declared as missed visits at the clinical discretion of the Investigator.

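### The live-vaccine bar ends at day 90, when the protocol's own figures suggest IL-18 is still almost fully suppressed; extending it to Visit 10 is a cheap precaution, and exclusion 19 should name the vaccine class

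*Protocol*

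**What the plan says.** Section 7.11.3 sets the rule during the trial: "Live, attenuated or recombinant vaccines are not permitted 60 days prior to GSK1070806 administration or within 90 days of treatment with GSK1070806". Its examples are nasal influenza and yellow fever vaccines. It then refers sites to the vaccine's summary of product characteristics (SmPC) and to the Trials Office clinical coordinator for advice.

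Exclusion 19 in section 4.2 sets the eligibility rule: "Participant has received live, attenuated or recombinant vaccine(s) within 2 months of randomisation or will require vaccination within 3 months of trial drug infusion". The class is named in the part before randomisation. It is not repeated in the part after infusion.

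Section 1.2.3 describes how long the drug acts on its target:
- in plasma, suppression was reached at low doses, "with 99.9% occupancy sustained for 90 days at a dose of 0.3mg/kg in the FTIH study";
- in the gut, a model predicts that "a dose of 10 mg/kg is required to maintain >99% IL-18 suppression in the gut interstitium for 90 days". For a tenfold lower dose, 1 mg/kg, the same section puts gut suppression above 90%.

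Section 1.1.4 explains why the target matters for infection: "IL-18 primes both innate and acquired immunity to viruses and other intracellular pathogens". The last assessment (section 7.13.7) is the "End of Study Visit 10 (Day 168 +/- 7 days. Week 24") visit. Section 6.1.1 adds that "Protocol waivers or exemptions are not allowed with the exception of immediate safety concerns".

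**The concern.** A bar on live vaccines after an immunomodulator should outlast the drug's effect on the relevant immunity. Here the bar ends on the last day for which section 1.2.3 gives a suppression figure, and that figure is near-complete suppression. Nothing in the protocol describes recovery by day 90 or explains why the bar stops there.

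The stake is first the patient. Section 1.1.4 gives IL-18 a role in defence against viruses, and both vaccine examples in 7.11.3 are directed at viruses. Patients may also be taking oral corticosteroids, azathioprine, methotrexate or 6-mercaptopurine under section 7.11.1. The second stake is the data. The frequency, type and severity of infections belong to the primary outcome (section 2.2), and adverse events are collected to Visit 10 (section 8.1.2). A vaccine-strain infection after day 90 would enter a comparison of about 14 patients with 7.

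A smaller point concerns exclusion 19. Taken literally, its second part excludes anyone due any vaccine within 3 months of infusion, including an inactivated one, which 7.11.3 does not bar.

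**Working it through.** **1. The two end dates.** The bar ends 90 days after treatment (7.11.3). The stated gut suppression above 99% at 10 mg/kg runs for 90 days (1.2.3). Margin: 90 − 90 = 0 days. The 3 months in exclusion 19 come to 89 to 92 calendar days, so they add no real margin.

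**2. Does suppression outlast day 90? No half-life is needed for this step.** The trial dose is 10/0.3 = 33.3 times the dose that still gave 99.9% plasma occupancy for 90 days. If a larger dose leaves at least as much drug at each time point, occupancy at day 90 after 10 mg/kg is at least as high. In the gut the model is still above 99% at day 90. An abrupt recovery on the next day is not plausible.

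**3. How much longer? Illustration only.** The protocol gives no half-life, so h is assumed at 7 to 35 days. Assume also dose-proportional kinetics with one terminal half-life, and that the 1 mg/kg gut figure refers to the same 90 days.
- Plasma: log2(10/0.3) = 5.06 half-lives. The level that 0.3 mg/kg leaves at day 90 is reached after 10 mg/kg at day 90 + 5.06h.
- Gut: log2(10/1) = 3.32 half-lives. The level that 1 mg/kg leaves at day 90 (suppression above 90%) is reached at day 90 + 3.32h.

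| Assumed half-life (days) | Plasma, 99.9% occupancy until about day | Gut, above 90% until about day |
|---|---|---|
| 7 | 125 | 113 |
| 14 | 161 | 137 |
| 21 | 196 | 160 |
| 28 | 232 | 183 |
| 35 | 267 | 206 |

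All of these lie beyond day 90. Faster clearance at low concentrations would bring them forward.

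**4. Consistency check.** Take a simple occupancy model C/(C + K) set to exactly 99% gut suppression at day 90 for 10 mg/kg, so that C/K = 99. At 1 mg/kg, C/K = 9.9 and suppression is 9.9/10.9 = 90.8%, in line with the protocol's figure of more than 90%. Run forward with h of 14 to 35 days, suppression on day 91 is 98.9% to 99.0%.

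**5. What Day 168 would achieve.** Time gained: 168 − 90 = 78 days, and 78/168 = 46% of follow-up. Day 168 reaches the plasma level in step 3 only if h is at most 78/5.06 = 15.4 days, and the gut level only if h is at most 78/3.32 = 23.5 days. In the model of step 4, gut suppression on Day 168 would be about 68%, 88%, 93% and 95% for h = 14, 21, 28 and 35 days.

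**6. Who is affected.** With 2:1 allocation, 21 × 2/3 = 14 patients receive the drug and 7 receive placebo. These are counts of patients in each arm. The protocol gives no rate at which they would receive a live vaccine between days 91 and 168.

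**The case against.** The strongest reply is that occupancy is not vulnerability. Section 1.2.3 reports the maximum ex-vivo effect, in particular on IFN-γ, only up to day 56, with no clear difference between 1 and 3 mg/kg. Section 1.1.7 reports no difference in infections against placebo after single doses up to 10 mg/kg in 57 participants. The pathogen study cited in section 1.1.4 was in mice. Section 7.11.3 also sends sites to the SmPC and the clinical coordinator, and the Investigator Brochure, which is not shown, may support day 90. On this view, a bar that covers the whole period of claimed suppression is a coherent choice, and Day 168 is no better supported.

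Much of this stands. A reader might infer that the protocol knowingly exposes patients to vaccine-strain infection, or that a harmful error has been shown. The documents do not support that, because the clinical risk is unquantified. Two limits apply to the reassurance. The 57 participants were healthy or obese volunteers, and section 1.1.7 does not mention live vaccination. The ex-vivo result concerns doses below the trial dose, and the text does not say whether day 56 was simply the last sample. Advice on request is useful, but it does not replace a rule.

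A reader might also take Day 168, or the 180-day contraception period in section 7.12, as the time by which IL-18 function recovers. Neither is offered as such. Day 168 is when follow-up ends, and contraception serves another purpose.

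On exclusion 19, the word for vaccination in the second part can sensibly be read as carrying over the class named in the first. Reading it so is interpretation and needs no waiver, so section 6.1.1 does not force the wide reading. The wide reading also costs eligibility and not safety. The point is therefore minor.

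**Conclusion.** The point holds as a precautionary safety improvement. The bar ends with no margin beyond the period of stated near-complete suppression, and suppression very probably continues past it. That conclusion rests on the protocol's own figures and on the assumption that a larger dose leaves at least as much drug. It does not depend on a half-life.

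The duration does. The projected days, 113 to 267 across assumed half-lives of 7 to 35 days, show a direction and cannot be used to set a recovery date. The size of the clinical risk cannot be derived from the protocol. Sample size and error rates are not affected.

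The wording of exclusion 19 is a minor inconsistency with 7.11.3. It would not be right to say that the protocol certainly excludes patients due an inactivated vaccine. It does so only on a literal reading, and eligibility text should not leave that choice to sites.

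**What to change.** **Section 7.11.3.** Replace the rule with: *Live or attenuated vaccines must not be given from 60 days before trial drug administration until Visit 10 (Day 168). Recombinant vaccines must not be given from 60 days before until 90 days after trial drug administration.* Keep the referral to the SmPC and the clinical coordinator.

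**Exclusion 19.** Replace the part on future vaccination with: *or will require a live or attenuated vaccine before Visit 10 (Day 168), or a recombinant vaccine within 90 days of trial drug infusion.*

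**Cost.** Two sentences in the protocol and matching patient information. No new data are needed, because concomitant medication is already reviewed to Visit 10. An elective live vaccine is deferred by up to 168 − 90 = 78 days, or 175 − 90 = 85 if Visit 10 falls at the end of its window. Because treatment is blinded, this applies to the roughly 7 placebo patients as well. A patient known to need a live vaccine between day 91 and Day 168 becomes ineligible, which matters a little in a trial of 21. Nobody waits longer for a recombinant vaccine, and patients due an inactivated one clearly remain eligible.

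If the sponsor has data showing that day 90 is safe, for example in the Investigator Brochure, stating that reason in 7.11.3 would be an acceptable alternative to the longer bar.
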